8.13.2. Non-Serious Adverse Event Reporting Requirements

All AEs will be reported on the AE page(s) of the CRF. It should be noted that the form for collection of SAE information is not the same as the AE CRF. Where the same data are collected, the forms must be completed in a consistent manner. For example, the same AE term should be used on both forms. AEs should be reported using concise medical terminology on the CRFs as well as on the form for collection of SAE information.

8.13.3. Sponsor Reporting Requirements to Regulatory Authorities

Adverse event reporting, including suspected unexpected serious adverse reactions, will be carried out in accordance with applicable local regulations.

9. DATA ANALYSIS/STATISTICAL METHODS

Detailed methodology for summary and statistical analyses of the data collected in this study will be documented in a Statistical Analysis Plan, which will be maintained by the Sponsor. This document may modify the plans outlined in the protocol; however, any major modifications of the primary endpoint definition and/or its analysis will also be reflected in a protocol amendment.

9.1. Sample Size Determination

The statistical objectives with respect to the primary safety endpoints, that is, malignancy (excluding non-melanoma skin cancer), and MACE, include drawing inferences with 95% (two-sided) confidence that the hazard ratios of the combined tofacitinib regimens versus the TNFi control regimen are less than 1.8. Assuming that the true hazard ratio is 1.0 the required number of events is 138 for malignancies to achieve 90% power and 103 for MACE to achieve 80% power.

The planned enrollment is approximately 4000 patients within 3 years (1000 in the first year and 1500 per year in the second and third years of recruitment). The assumed 'dropout or Loss to Follow-up' (LTFU) rate for MACE is 10% in the first year, 7% in the second and 5% per year, thereafter. For malignancies, because they will be followed after discontinuation the LTFU rate is assumed to be 5% in the first year, 3.5% in the second year and 2.5% per year thereafter. The assumed event rate for MACE is 1.0 event per hundred patient-years and the assumed rate for malignancy is 1.1 events per hundred patient-years; assumptions are based on results from the CORRONA database,²⁰ and also based on a meta-analysis of TNF- α inhibitors.²¹ Based on those assumptions it is expected that the trial will accrue the desired number of events in approximately 5 years.

Additionally, the statistical objectives with respect to the primary safety endpoints include drawing inferences with 95% (two-sided) confidence that the hazard ratios of the tofacitinib 10 mg regimen to the tofacitinib 5 mg regimen are less than 2.0. Assuming that the true hazard ratio is 1.0 the required number of events is 87 for malignancies to achieve 90% power and 65 for MACE to achieve 80% power. Based on the same assumptions of patient enrollment, LTFU and event rates, the trial is expected to accrue the desired number of events in approximately 5 years.

The trial will conclude when the required number of events (138 malignancies and 103 MACE) has been observed. It is likely that more than the required events may be observed in one endpoint in order to get the required event in another, therefore the power may be higher for a given endpoint (eg, more than 103 MACE events may need to be observed in order to observe 138 malignancy events). The final analysis will utilize all observed events.

Software for sample size and power calculation was East 5®, Cytel Inc, Boston, MA, USA.

9.2. Safety Analysis

9.2.1. Analysis of Primary Safety Endpoint

The co-primary safety endpoints of malignancies and MACE will be analyzed to provide comparative rates for tofacitinib vs. the combined TNFi.

The primary statistical safety objective is the estimation of the hazard ratios relative to the TNFi control for the two tofacitinib doses combined and for each dose of tofacitinib separately for the adjudicated events of MACE and malignancy excluding non-melanoma skin cancer. Analysis of the primary safety endpoints will be based upon adjudicated events.

Hazard ratios for the safety events of main interest will be calculated separately for each primary endpoint. The ratios for both tofacitinib doses combined versus the control, for each tofacitinib dose versus the control, and for the two tofacitinib doses versus each other will be reported along with their 95% confidence intervals. Adjustments for multiplicity will not be applied.

The primary statistical method for deriving estimators for hazard ratios will be the fitting of proportional hazards (Cox) regression models. A model containing only the single independent variable for treatment group will be calculated and reported. The effects of adding other predictors to the model, such as geographic region, age, gender, and so forth will be fully explored and reported. An analysis by TNFi subset strata (ie, the sites/regions where either adalimumab or etanercept was used) will be conducted to assure consistency of results.

A Surveillance, Epidemiology, and End Results (SEER) analysis of the malignancy endpoint will be conducted.

Both total time (or ITT) and on treatment analyses of the main safety endpoints will be conducted. The total time analysis will not censor times to event and will ascribe events to randomized treatment.

The on-treatment analysis for MACE will censor subjects who crossover from tofacitinib, adalimumab or etanercept to standard of care at 60 days after standard of care is initiated. The principal analysis for malignancies will not censor for subjects crossing to standard of care (ie, will be the total time analysis).

9.2.2. Analysis of Secondary Safety Endpoints

The secondary safety endpoints will include an evaluation of the following events:

- Opportunistic infection events including tuberculosis (adjudicated).
- Hepatic events (adjudicated).
- Cardiovascular events other than MACE (adjudicated).
- All AEs, including SAEs.
- Clinically significant abnormal laboratory parameters.
- All cause mortality (adjudicated).
- Reasons for permanent or temporary discontinuation of study medication.

Adverse events and clinical laboratory abnormalities ([Section 2.2.1.2](#)) will be summarized according to treatment received at the time of the event. Both ITT and on treatment analyses will be conducted for the other secondary endpoints listed in [Section 2.2.1.2](#).

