2.2.1.2. Secondary Safety Endpoints

The secondary safety endpoints will include an evaluation of the following events:

- Opportunistic infection events including tuberculosis (adjudicated).
- Hepatic events (adjudicated).
- Cardiovascular events other than MACE (adjudicated).
- All adverse events (AEs), including serious adverse events (SAEs).
- Clinically significant abnormal laboratory parameters.
- All cause mortality (adjudicated).
- Reasons for permanent or temporary discontinuation of study medication.

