13.7. Subject Retention Performance Standard

The purpose of this performance standard is to identify subject retention performance standards and to define the actions to be taken if the performance standard is not met.

The performance standard for subject retention within their assigned treatment group is an assigned treatment discontinuation rate of approximately 15% annually during the conduct of the study with higher discontinuation rates seen during the first year of the study.

The expected assigned treatment discontinuation rates were developed from overall discontinuation rates seen in tofacitinib RA Phase 2/3 studies and the Long-Term Extension Studies and have been applied to this study as the projected performance standard for subject retention within their assigned treatment group.

Discontinuation rates, including reason for discontinuation, are collected and reviewed by the study clinician periodically during the study. Discontinuation rates will be evaluated at least monthly for trends in total rates and components of these rates (eg, adverse events, insufficient clinical response, no longer willing to participate).

This study is being managed by an Alliance Partner. The Alliance Partner will have risk/mitigation plans in place to identify specific remedial actions to be taken, depending on the reason for the increased rate in discontinuation; these actions will be implemented if the rate of discontinuation exceeds the performance standard. However, intermediate interventions may be applied if component rates are trending upwards and reasons can be identified and addressed by the study team (eg, inappropriate subject selection, retraining of

sites, etc) (CTPQS-106 Plan and Manage Study Execution, Version 3, Effective Date: 15-Feb-2013).

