8. STATISTICAL METHODOLOGY AND STATISTICAL ANALYSES

In general, number and percent will be presented for binary variables, number, mean, standard deviation (standard error of the mean), minimum, 1st, 2nd and 3rd quartiles and maximum will be presented for continuous variables. In addition, graphics may be used to present the data.

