8.2.2. Analyses of Other Safety Endpoints

The analyses will be based on the Safety Analysis Set. The 28-Day On-Treatment Time will be applied to all the events of interest, see [Section 7.1.1](#).

The times to the secondary endpoints of opportunistic infection events excluding tuberculosis, tuberculosis, hepatic events, cardiovascular events (MACE and others), serious infections, GI perforations, non-melanoma skin cancers, interstitial lung disease, DVT, PE, ATE, DVT or PE, thromboembolic events (TE) and all-cause mortality will be analyzed by Cox models via univariate model analysis. See [Section 8.1.1](#). The 28-Day On-Treatment Time analysis will be conducted.

The times to herpes zoster events will be analyzed by a multivariate Cox model with region, baseline corticosteroid use, age group, smoking status, treatment as predictors. The 28-Day On-Treatment Time analysis will be conducted.

Unadjusted, or “crude” incidence rates will be calculated as well. Note that the ratios of these rates approximate, but are not exactly equal to, the hazard ratios.

A Surveillance, Epidemiology, and End Results (SEER) analysis of the malignancy endpoint will be conducted. In this analysis, standardized incidence ratio (SIR) for malignancies represents the ratio of the incident number of cases of cancer in the tofacitinib population to the incident number that would be expected if the study population had the same incidence rate as the US population. By way of interpretation, a SIR of more than 1.0 indicates that proportionally more cases of cancer have occurred in the tofacitinib population than the comparator, whereas a SIR of less than 1.0 indicates that proportionally fewer cancer cases have occurred.

The Sponsor has standard (ie, used for all its clinical trials) summary displays and listings for MedDRA-coded adverse events, demography, medical history, length of time in study and discontinuation, concomitant and concurrent medications, physical examination, ECG, laboratory tests, weight, pulse rate, and blood pressure. These standards, called *CaPS (CDISC and Pfizer Standards)*, will be utilized in the reporting of these routine safety variables. For laboratory tests total cholesterol, LDL-c, HDL-c, total cholesterol/HDL-c ratio, LDL-c/HDL-c ratio, Triglyceride, the summary will be produced by subjects on statins, subjects not on statins and subjects on any lower lipid agents including statins.

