Only treatment emergent adverse events (TEAE) will be summarized. An event is considered TEAE if the event occurs for the first time during the effective duration of treatment and is not seen prior to the start of treatment or the event is seen prior to the start of treatment but increase in severity during treatment.

No inferential analysis is pre-planned for this set of variables.

These standard summaries of routine safety and subject characteristic data will be organized according to initially randomized group, ie, tofacitinib 5 mg BID, tofacitinib 10 mg BID, tofacitinib combined, and TNFi combined.

For the summaries of TEAE, the treatment emergence for the standard of care will be derived comparing events that happen after switching to the standard of care with events that happen before switching including those after the first dose of randomized treatment.

For subjects who switch from the randomized treatment to standard of care, a separate TEAE table will be presented for these subjects according to their initially randomized group.

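### SAP 8.2.2 does not clearly assign a person-time rate to overall AEs and SAEs, so their on-treatment percentages could favour an arm whose subjects stop drug sooner

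*Protocol*

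**What the plan says.** Protocol 2.2.1.2 lists all AEs, including SAEs, as a secondary safety endpoint. Protocol 9.2.2 says that AEs and laboratory abnormalities "will be summarized according to treatment received at the time of the event". The next sentence, "Both ITT and on treatment analyses will be conducted for the other secondary endpoints", covers only the rest of the list, so AEs have no stated total-time counterpart.

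The SAP adds the following:

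- SAP 8 (opening): "In general, number and percent will be presented for binary variables".
- SAP 8.2.2: "Only treatment emergent adverse events (TEAE) will be summarized". An event counts "if the event occurs for the first time during the effective duration of treatment" (or if a pre-existing event worsens), and that duration is given no number of days.
- SAP 8.2.2: Cox models cover a named list (opportunistic infections, tuberculosis, hepatic and cardiovascular events, serious infections, thromboembolic events, all-cause mortality and others), with a separate model for herpes zoster. Overall AEs and overall SAEs are not named. Crude incidence rates are announced next, followed by "Note that the ratios of these rates approximate, but are not exactly equal to, the hazard ratios".
- SAP 8.2.2: MedDRA-coded AEs then go to the sponsor's standard displays, by initially randomized group and with no inferential analysis planned. Subjects who switch to standard of care have a separate table.
- SAP 7.1.1: the 28-Day On-Treatment Time is said to serve all secondary safety endpoints.
- SAP 6.2: patient-years of exposure are listed by arm, including standard of care.

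Protocol 13.7 expects "an assigned treatment discontinuation rate of approximately 15% annually", higher in the first year.

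**The concern.** Enrollment runs over 3 years and the study is expected to end at about 5, so potential follow-up ranges from about 2 to 5 years, and assigned drug is stopped along the way. The percent of subjects with an on-treatment event then depends on two things: how often events occur and how long subjects remain on drug. If one arm stops sooner, its subjects have less time in which to be counted, and its percentage falls with no difference in risk.

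In a post-authorization safety study, readers will set the overall AE and SAE tables side by side across arms whether or not a test is attached. The switcher table has the same difficulty, because time on standard of care varies from subject to subject.

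Elsewhere in SAP 6.2 an incidence rate is requested by name: for tuberculosis, herpes zoster, GI perforations and deaths. The entry for all AEs and SAEs carries no such request.

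**Working it through.** The documents give no expected AE or SAE figure, so there is no plan figure to reproduce. The check asks how far an on-treatment percent can move when the true event rate is the same in every arm.

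**Inputs from the plan**

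- Accrual of 1000, 1500 and 1500 in years 1 to 3, with the end at 5 years (Protocol 9.1). Mean administrative follow-up is (1000×4.5 + 1500×3.5 + 1500×2.5)/4000 = 3.375 years.
- Loss from the study of 5%, 3.5%, then 2.5% per year (Protocol 9.1, malignancy figures, which apply to follow-up after discontinuation).
- Stopping of assigned drug at about 15% per year (Protocol 13.7). It is taken as constant, although the protocol expects more in year 1.

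**Assumptions**

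- SAE hazard λ of 5, 10 or 20 per 100 patient-years (PY), constant and equal in all arms.
- Stopping at 18%, 20% or 25% per year in a second arm.
- Stopping independent of events.

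**Formula**

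With stopping hazard d = −ln(1 − p), study retention L(t), and A(t) the share of subjects whose administrative follow-up exceeds t, the mean time at risk to first on-treatment event is

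M = ∫₀⁵ exp(−λt) · exp(−dt) · L(t) · A(t) dt,

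and the percent with an event is 100·λ·M.

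**Results at λ = 0.10 per year**

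| Stopping per year | d | M (years) | Percent with on-treatment SAE | Rate per 100 PY |
|---|---|---|---|---|
| 15% | 0.163 | 2.07 | 20.7% | 10 |
| 18% | 0.198 | 1.97 | 19.7% | 10 |
| 20% | 0.223 | 1.90 | 19.0% | 10 |
| 25% | 0.288 | 1.74 | 17.4% | 10 |

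Relative to 15% stopping, 18% gives 19.7/20.7 = 0.95 and 25% gives 17.4/20.7 = 0.84. Per 1300 subjects the gaps are about 13 and 43. At λ = 0.05 the 15% and 25% figures are 11.1% and 9.3%; at λ = 0.20 they are 36.1% and 30.8%. With equal stopping the percentages are equal. Adding a 28-day window after the last dose changes 20.7% and 17.4% to about 21.0% and 17.8%.

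**Masking case**

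An arm stopping at 25% with a true hazard of 0.12 has M = 1.70 and shows 0.12 × 1.70 = 20.4%. This sits beside 20.7% for an arm stopping at 15% with hazard 0.10. The 1.2-fold excess is not visible in the percentages.

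**Hand check**

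With everyone followed 3.375 years and no study loss, M = (1 − exp(−(λ+d)·3.375))/(λ+d). At λ = 0.10 this gives 2.24 (22.4%) for 15% stopping and 1.88 (18.8%) for 25%, a ratio of 0.84.

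**The case against.** A reader might infer that the plan compares arms on percent alone and so builds in a bias that hides harm. The documents do not support that, for four reasons.

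- *No inference is planned on these tables.* They are descriptive. Formal between-arm safety analysis uses Cox models for MACE, malignancy and the named secondary events. This stands.
- *Percent-only is an inference.* The Protocol 9.2.2 sentence is a grouping rule and names no measure. The number-and-percent sentence is a general one, and the sponsor's standard displays are not reproduced, so they may contain rate columns. SAP 7.1.1 applies the 28-day clock to all secondary safety endpoints, and SAP 8.2.2 applies it to all events of interest and then promises crude rates. That can be read as already covering overall AEs and SAEs. Against it, the crude-rate sentence is tied to endpoints that have hazard ratios, and a censoring rule does not specify what a table reports. The text is ambiguous.
- *Unequal stopping is assumed.* The single documented rate is not split by arm. The trial is open-label and only the 10 mg BID arm had its dose changed mid-study, so a difference is possible, but its size is unknown. The masking case depends on choosing 25%.
- *Stopping may be related to events.* A subject who stops because of an on-treatment AE has already been counted, so the model overstates the distortion for such events. If stopping is informative in other ways, an on-treatment rate is affected too.

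The patient-years in SAP 6.2 help only partly. They are listed as exposure totals, not as time at risk to a first event, and the switcher table has no stated denominator.

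**Conclusion.** The point holds as a gap in specification. Overall AEs and SAEs are counted only while on treatment, and neither document clearly gives them a person-time rate. Their percentages will favour an arm that stops sooner, by about 5% relative at 15% versus 18% stopping and about 16% at 15% versus 25%. Those sizes rest on assumed constant hazards, assumed stopping rates by arm, and stopping independent of events; at equal stopping the effect is zero.

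Two textual problems add to it. The treatment-emergent window has no stated length. Protocol 9.2.2 groups AEs by treatment received at the event, whereas SAP 8.2.2 groups them by initially randomized arm. The documents do not show that any planned comparison is biased or that a safety signal would be missed.

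**What to change.** In SAP 8.2.2:

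- State that the crude first-event incidence rates of SAP 8.1.2 also cover all AEs, all SAEs and AEs leading to discontinuation. Use the 28-Day On-Treatment Time, per 100 patient-years, by randomized group, with the exact Poisson limits, shown beside number and percent. Rate columns for system organ classes and preferred terms can be optional.
- Give the switcher table a denominator of patient-years on standard of care.
- State the length in days of the effective duration of treatment, so that numerator and time at risk use the same window.
- Reconcile the grouping rule with Protocol 9.2.2.

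The cost is a few sentences and some table columns, since the clock, the interval method and exposure by arm are already in the SAP. The downsides are longer tables and rates that assume a roughly constant hazard and non-informative stopping.

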9.3. Efficacy Analysis

Efficacy endpoints will include:

- Change from baseline to each post-baseline scheduled visit in DAS28-4 (CRP), Simplified Disease Activity Index (SDAI) and Clinical Disease Activity Index (CDAI).
- Rate of remission at each post-baseline scheduled visit including:
 - ACR-EULAR Boolean remission (defined as the subject satisfying all of the following: tender joint count ≤ 1 , swollen joint count ≤ 1 , CRP ≤ 1 mg/dL, patient global assessment ≤ 1 on a 0-10 scale).
 - SDAI ≤ 3.3 .
 - CDAI ≤ 2.8 .
- Rate of low disease activity (LDA) at each post-baseline scheduled visit including:
 - SDAI ≤ 11 .
 - CDAI ≤ 10 .
 - DAS28-4(CRP) ≤ 3.2 .
- ACR20, ACR50, and ACR70 response rate of at each post-baseline scheduled visit.
- Change from baseline to each post-baseline scheduled visit in the HAQ-DI.

Descriptive statistics of efficacy endpoints for all subjects in the study will be provided from baseline to the declared end of the study. Differences between each tofacitinib regimen and the TNFi regimen, as well as between tofacitinib regimens, will be estimated.

Details may be found in the statistical analysis plan.

9.4. Interim Analysis

No interim analysis of the study data will be performed for use outside the DMC and the Steering Committee.

9.5. Data Monitoring Committee

This study will use an external Data Monitoring Committee (DMC).

The DMC will be responsible for ongoing monitoring of safety of subjects in the study in an unblinded manner according to the Charter. All safety data, including potential primary endpoint data will be forwarded to, and reviewed by, the DMC on a regular basis. Based on these reviews, the DMC will have the capacity to make recommendations to Pfizer that might impact the future conduct of the trial. The recommendations made by the DMC to alter the

conduct of the study will be forwarded to Pfizer and the Steering Committee for final decision. Pfizer will forward such decisions, which may include summaries of aggregate analyses of endpoint events and of safety data which are not endpoints, to regulatory authorities, as appropriate.

9.6. Steering Committee

The Steering Committee is a committee established by Pfizer to oversee the conduct of the trial, assess at intervals the progress of a clinical trial (ie, Performance Standards), the aggregate accumulation of primary endpoint events (ie, MACE and malignancies) meeting pre-specified criteria, and the attainment of 1500 subjects completing 3 years in the study. The Steering Committee will recommend to the study team whether to continue, modify or stop a trial, independently from the study team. The Steering Committee will include only non-Pfizer trial experts who are not members of the study team.

The Steering Committee will consider the ongoing accumulation of the adjudicated primary endpoint events and study performance standard metrics and may determine that sufficient events have occurred to assess the primary objectives of the study or that it is not feasible to continue the trial in pursuit of the stated objectives. These determinations by the Steering Committee will be made in accordance with pre-specified rules documented in the Steering Committee Charter and in the Statistical Analysis Plan and following consultations with the US FDA could result in recommendations for changes in study design, including changes in number of subjects studied or duration of study.

The Steering Committee Charter will pre-specify all reviews of the data that will be performed during the conduct of the study and how the data will be evaluated to determine that study completion can be declared.

The Steering Committee will be responsible for blinded review of adjudicated, aggregate primary endpoint data according to its charter.

Any recommendations made by the Steering Committee to alter the conduct of the study will be forwarded to the study team who will confer with the US FDA prior to implementation of any changes in the study design. Pfizer will forward such decisions, which may include summaries of aggregate analyses of endpoint events and of safety data which are not endpoints to regulatory authorities, as appropriate.

The numbers of events necessary to achieve the targeted statistical power for the comparisons of the hazards for the primary endpoints with respect to the various combinations of treatment groups and boundaries were given in a previous section of this protocol.

Additionally, the Steering Committee will maintain detailed Performance Standards (refer to [Section 13](#)), periodically review metrics and implement corrective actions, as needed.

